8.1.1 HCP recruitment

HCPs include both physicians and nurses.

- A) Physicians: A target list of physicians known to be prescribing Fabrazyme home infusion will be provided by the MAH and used for recruitment. Potentially eligible physicians will be approached via telephone or email with information about this study. The method of contacting physicians is dependent on contact details provided in the target list.
- B) Nurses: Based on information provided by the MAH, Nurses play an important role in providing in person medical supervision and education to patients receiving Fabrazyme home infusion in the UK, France, Italy and Finland. Therefore nurses will be included in the HCP sample in these markets. To recruit nurses we will use a mix of both targeted recruitment and via physician referral; for targeted recruitment the MAH will provide a list of external home care provider companies with contact details per market. Potentially eligible nurses will be contacted via telephone or email with information about this study. The method of contacting nurses is dependent on contact details obtained via the physicians or home care providers.

To increase participation in the survey all HCPs on the target lists will be sent a letter of endorsement from the MAH and MAH representative that provides information to validate the regulatory requirement associated with the reason for the survey. Interested HCPs will be asked screening questions to check eligibility for the survey.

Inclusion/exclusion criteria:

- Involved in the treatment of at least 1 patient with Fabry disease in the last 12 months
- Have prescribed Fabrazyme for home infusion and/or monitor, oversee the management, and/or provide in person medical supervision of patients on Fabrazyme home infusion in the last 12 months
- Not a current or ex-employee of Sanofi

If the criteria are met, HCPs are asked to provide consent to participate in the study. Once consent has been provided HCPs is provided with a link to access and complete the main survey.

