8.2 SETTING

The surveys will be conducted in 5 countries (France, UK, Italy, Finland and Norway). [Table 1](#) below shows the home infusion patient and prescriber numbers for the 10 markets in which Fabrazyme home infusion is most prevalent as provided by MAH.

Table 1 - Approximate number of patients and prescribers for top 10 countries based on data provided by the MAH, as of February 2017

Country	Potential home infusion prescribers	Fabrazyme home infusion patients
France	30	140
UK	20	190
Italy	10	65
Finland	15	27
Norway	8	34
Germany	5	7
Spain	1	1
Netherlands	1	35
Sweden	3	10

Country	Potential home infusion prescribers	Fabrazyme home infusion patients
Belgium	5	10
TOTAL	98	519

The countries selected for this study had the highest number of prescribers of Fabrazyme home infusion or patients receiving Fabrazyme in the home setting based on the data in table 1. There are:

- 98 prescribers of Fabrazyme home infusion and 83 of these (85%) were based in France, UK, Italy, Finland and Norway.
- 519 Fabrazyme home infusion patients and 456 of these (88%) were based in France, UK, Italy, Finland and Norway.

Other markets (Germany, Spain, Netherlands, Sweden and Belgium) only had a maximum of 5 prescribers of Fabrazyme home infusion.

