8.7 DATA ANALYSIS

The analysis will be cross-sectional and descriptive. Categorical data will be summarized by counts and percentages. Continuous data will be summarized using number, median, minimum and maximum values. Missing data will be noted for each variable.

A **positive outcome** reported across key pre-defined questions for each of these objectives would support the effectiveness of the educational material. For this assessment, a positive outcome is defined as at >70% of the survey participants providing a ‘correct’ response (specific questions and responses are outlined in Tables [Table 8](#) and [Table 9](#)). The 70% cut point is based on previous experience from other surveys evaluating the effectiveness of educational materials.

Table 8 - Questions to assess effectiveness in HCP survey

Category of assessment	Question text [Answer options]	Criteria for 'effective assessment'
To assess if materials are being received and read	A2. Which of the following material have you received or had access to? Select all that apply 1. Summary of Product Characteristics (SMPC) 2. Fabrazyme Home Infusion Therapy: A guide for Healthcare professionals treating patients with Fabry disease 3. Fabrazyme Home Infusion Therapy: Manual for Patients with Fabry disease who receive home infusion of Fabrazyme 4. None of the above	Majority of HCPs selecting Code 2
	A3. Have you read the Fabrazyme (agalsidase beta) home infusion educational materials? 1. Yes 2. No	Majority of HCPs selecting Code 1
To assess evaluation of home infusion	B1. Do you use the educational materials to evaluate and select patients for home infusions? 1. Yes 2. No	Majority of HCPs selecting Code 1
	B2. Which of the following criteria must be fulfilled before a patient is deemed eligible for Fabrazyme (agalsidase beta) home infusion? Select all that apply 1. Patient must be medically stable 2. A comprehensive evaluation must be completed before deciding on transfer of therapy to home infusion 3. Patient must have received Fabrazyme infusions for several months in a controlled setting and previous infusions well tolerated 4. Don't know	Majority of HCPs selecting codes 1, 2 and 3
To assess level of training to patients/caregivers	B4. Do you use the Fabrazyme (agalsidase beta) home infusion educational materials when training the patient/caregiver on the home infusion process? 1. Yes 2. No	Majority of HCPs selecting Code 1

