	B5. How frequently do you cover each of the following areas when training the patient/caregiver on Fabrazyme home infusion? [1. Always / 2. Regularly / 3. Rarely / 4. Never] a. Importance of adhering to the pre-defined infusion schedule (dose and infusion rate) b. Method of preparation, reconstitution and administration c. Instructions for handling Adverse Events (AEs) and Infusion Associated Reactions (IARs) d. Completing the logbook	Majority of HCPs selecting codes 1 & 2 for each area
To assess knowledge on actions taken in case of IAR and AE	B6. In the event of an infusion associated reaction (IAR) what are the appropriate steps that should be taken? Select all that apply 1. Infusion is immediately discontinued	Majority of HCPs selecting codes 1 & 3

	
2. Infusion is completed and IAR recorded in the logbook
 
3. Patient/Infusion nurse to call the treating physician immediately
 
4. Don't Know
	
To assess implementation of logbook	
C1. How often do you clearly state the Fabrazyme (agalsidase beta) home infusion administration details in the logbook of your Fabry patients? [1. Always / 2. Regularly / 3. Rarely / 4. Never]
	Majority of HCPs selecting codes 1 & 2
	
C2. How often do you review your patients' logbooks? [1. Always / 2. Regularly / 3. Rarely / 4. Never]
	Majority of HCPs selecting codes 1 & 2
	
C4. Considering the logbook, how often do you do each of the following: [1. Always / 2. Regularly / 3. Rarely / 4. Never]
 
a. Document changes to the infusion schedule
 
b. Check the infusion rate
 
c. Check the dose administered
 
d. Discuss logbook with patient/caregiver
	Majority of HCPs selecting codes 1 & 2 for each element

Table 9 - Questions to assess effectiveness in patients/caregivers survey

Category of assessment	Question text [Answer options]	Criteria for 'effective assessment'
To assess if materials are being received read and referred to	
A2. Have you [or the person you care for] received any of the following? Select all that apply
 
1. Package leaflet for Fabrazyme
 
2. Fabrazyme Home Infusion Therapy: Manual for Patients with Fabry disease who receive home infusion of Fabrazyme
 
3. None of the above
	Majority of patients selecting Code 2
	
A3. Have you read the Fabrazyme (agalsidase beta) home infusion educational materials?
 
1. Yes
 
2. No
	Majority of patients selecting Code 1

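### HCP items B1, B4 and B5 score selecting and training patients over all survey participants, although HCPs can qualify without doing either and no not-applicable answer is printed

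*Protocol*

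**What the plan says.** Eligibility (Protocol 8.1.1). An HCP must be "Involved in the treatment of at least 1 patient with Fabry disease in the last 12 months" and must also "Have prescribed Fabrazyme for home infusion and/or monitor, oversee the management, and/or provide in person medical supervision of patients on Fabrazyme home infusion" within the same 12 months. The second criterion is an and/or list, so monitoring, overseeing or supervising is enough. The sample is mixed: "HCPs include both physicians and nurses".

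Scored items (Protocol 8.7, Table 8):
- B1 asks whether the HCP uses the materials to evaluate and select patients (Yes/No).
- B4 asks "Do you use the Fabrazyme (agalsidase beta) home infusion educational materials when training the patient/caregiver on the home infusion process" (Yes/No).
- B5 asks "How frequently do you cover each of the following areas when training the patient/caregiver on Fabrazyme home infusion", for four areas, each answered from Always to Never.

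None of the three prints a not-applicable code or a recall period.

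Scoring rule. The text of 8.7 defines a positive outcome as more than 70% of survey participants giving the correct response. Table 8 states no narrower denominator for these items. In Table 9, patient item C2 offers a code for no changes and removes those answers from the calculation.

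Sample size (Protocol 8.5.1). The target is 34 HCPs with at least 25 physicians, which leaves room for up to 9 nurses.

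**The concern.** The population that may answer is wider than the population that performs what is asked. An HCP who supervises infusions but neither selects nor trains patients has no accurate answer to B1, B4 or B5. No, or Never, enters the score as a failure of the materials; Yes, or Always, describes what the HCP would do. The first pushes the percentage down and the second pushes it up, and the reported percentage does not show which has happened.

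What to address in training is part of the primary objective (Protocol 7), and in Table 8 only B4 and B5 fall under the training category. B1 is one of two items for the evaluation objective; the other, B2, tests knowledge and is not affected.

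**Working it through.** **Inputs.** N = 34 (8.5.1) and the rule of more than 70% of participants (8.7). The documents do not give the number of HCPs without the activity, so k is varied as an assumption. The true favourable rates among HCPs who do the activity (85% for materials that work, 60% for materials that fall short) are also assumptions.

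**The plan's own figure.** Table 6 uses the half-width 1.96 × √(p(1−p)/n). With n = 34 and p = 0.70: 1.96 × √(0.21/34) = 15.4 points, as printed. The 80% and 60% rows also reproduce (13.4 and 16.5). No stated figure is in dispute.

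**Count needed.** 23/34 = 67.6% fails and 24/34 = 70.6% passes, so 24 favourable answers are needed.

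**Effect of k HCPs without the activity.** Let m = 34 − k.
- All k answer No and stay in: the others must supply 24 of m, and P(pass) = P(Bin(m, 0.85) ≥ 24).
- The k are excluded: P(pass) = P(Bin(m, 0.85) ≥ r), where r is the smallest count above 70% of m.
- All k answer Yes hypothetically, with materials that fall short: P(pass) = P(Bin(m, 0.60) ≥ 24 − k).

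| k | m | Rate needed among the others if k say No | P(pass), k say No, 85% | P(pass), k excluded, 85% (r) | P(pass), k say Yes, 60% |
|---|---|---|---|---|---|
| 0 | 34 | 24/34 = 71% | 0.99 | 0.99 (24) | 0.14 |
| 3 | 31 | 24/31 = 77% | 0.92 | 0.99 (22) | 0.25 |
| 5 | 29 | 24/29 = 83% | 0.74 | 0.98 (21) | 0.34 |
| 7 | 27 | 24/27 = 89% | 0.41 | 0.99 (19) | 0.46 |
| 9 | 25 | 24/25 = 96% | 0.09 | 0.97 (18) | 0.59 |

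From k = 11 only 23 HCPs remain, so 24 favourable answers cannot be reached if all k say No. With the k excluded and a true 60%, P(pass) stays between 0.12 and 0.18 for the k in the table, so exclusion does not make a pass easy.

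**Precision cost of exclusion.** With 25 HCPs left, 1.96 × √(0.21/25) = 18.0 points at 70%, against 15.4 with 34.

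**The case against.** **Routing may exist.** Table 3 lists a question on whether patients are trained on the home infusion process, just before the item on using the materials for training. Table 8 prints only scored items and goes from B2 to B4, so a B3 may send non-trainers past B4 and B5. The questionnaire is Appendix 1, which is not shown. This stands as a possibility. But no routing or denominator rule is stated, the Table 3 wording asks whether patients are trained rather than whether this HCP trains them, and it does not touch B1.

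**Many HCPs may well do the activity.** For every study country except Norway, the protocol says that "Nurses play an important role in providing in person medical supervision and education to patients receiving Fabrazyme home infusion". Prescribing is itself a qualifying route. Both points limit how large k is likely to be; neither makes it zero.

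**Undated answers are still informative.** The items ask about usual practice. A physician who used the guide when training a patient two years ago gives a valid Yes. This stands, and it is why the missing recall period is secondary here.

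**Stronger readings that a reader might infer.** Table 1 gives 456/83 = 5.5 home-infusion patients per prescriber, and 27/15 = 1.8 in Finland. From this one might infer that most physicians started nobody in the last 12 months, so that the training objective depends on distant or imagined practice. The documents do not support that. They give no rate of new starts, they do not say that training happens only once at the move home, and they describe nurses educating patients who are already receiving home infusion.

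**Conclusion.** The point holds as a defect in the scoring rule. Eligibility is wider than the activities scored in B1, B4 and B5. As printed, HCPs without the activity stay in the denominator with no accurate answer open to them, although the same protocol solves this problem for patient item C2.

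If 5 to 7 of 34 HCPs lack the activity and answer No, the chance of passing at a true 85% falls from 0.99 to between 0.74 and 0.41. If they answer Yes and the true rate is 60%, the chance of an undeserved pass rises from 0.14 to between 0.34 and 0.46. These figures assume independent answers, a uniform response among the k, and the more-than-70% rule applied item by item. How many HCPs are affected cannot be learned from the protocol, and routing in the unseen questionnaire may reduce the problem for B4 and B5. The matter is worth correcting because a few respondents can turn the result either way and the correction is small.

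**What to change.** 1. Add one answer code to B1, B4 and B5: not applicable, I do not select (B1) or train (B4, B5) patients for home infusion, or have not done so since having the guide.
2. State in Table 8 that these answers leave the denominator of the item concerned, as C2 in Table 9 already does. If the Table 3 training question routes B4 and B5, say so in the same place.
3. For each item, report how many HCPs had the opportunity, and show the all-HCP percentage beside the restricted one.
4. If wanted, collect the number of patients selected or trained, for description only. Twelve months without a new patient should not exclude anyone: it would discard valid answers about usual practice and could cost much precision. If it left 20 or 11 HCPs, for example, the half-width at 70% would be 1.96 × √(0.21/20) = 20.1 or 1.96 × √(0.21/11) = 27.1 points.

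The cost is one answer code on three items and one sentence in Table 8, before launch. The downside is smaller denominators: 25 instead of 34 widens the half-width at 70% from 15.4 to 18.0 points. Keeping the all-HCP figure alongside means that nothing now planned is lost.

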	
A5. How often do you [or the patient] refer to the educational materials when the home infusions are being done?
 
1. At every infusion
 
2. Frequently
 
3. Rarely
 
4. Never
	Majority of patients selecting Code 1 or 2
To assess knowledge on preparation of infusion	
B3. Which of the following statements are true in relation to the preparation, administration and storage of Fabrazyme. Select all that apply
 
1. The vials must be removed from the refrigerator approximately 30 mins before preparation
 
2. The reconstituted mixture should be shaken up
 
3. The reconstituted solution must be clear and colourless before use
	Majority of patients selecting Code 1, 3 & 4

	
4. The tourniquet should be applied to identify a vein
 
5. The product can be stored at room temperature for 48 hours before use
 
6. None of the above are true
 
7. N/A I don't prepare the infusion on my own
	
To assess knowledge on actions taken in case of AE	
C5. What would you do if [you / the patient] developed a headache and a fever during the infusion?
 
1. Complete the infusion and then rest
 
2. Immediately stop the infusion
 
3. Contact the physician
 
4. Record details in the logbook
 
5. Don't Know
	Majority of patients selecting Code 2, 3 and 4
To assess implementation of logbook	
C1. Considering the Fabrazyme (agalsidase beta) home infusion, how often do you or the nurse who helps you with the infusion (if applicable) do the following actions?
 
[1. Always / 2. Regularly / 3. Rarely / 4. Never]
 
a. Fill out the infusion data in the logbook
 
b. Take the logbook to each appointment with the prescribing physician
	Majority of patients selecting codes 1 & 2 for both actions
	
C2. How often do you or the nurse who helps you with the infusion report changes about the infusion (dose or infusion rate) in [your / the patient's] logbook?
 
1. Always
 
2. Regularly
 
3. Rarely
 
4. Never
 
5. N/A There have been no changes
	Majority of patients selecting codes 1 or 2 (excluding those selecting code 5 from calculation)
	
C6. If [you / the patient] had a side effect, should you report the side effect in your log book?
 
1. Yes, always
 
2. Only if I think it's serious
 
3. No, it is not necessary
	Majority of patients selecting codes 1

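### Knowledge items HCP B6, patient B3 and patient C5 define a correct answer only by the codes that must be ticked, so read literally a respondent who also ticks an unkeyed statement still counts toward the >70% threshold

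*Protocol*

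**What the plan says.** Protocol section 8.7 sets the decision rule: "a positive outcome is defined as at >70% of the survey participants providing a" correct response. It refers to Tables 8 and 9 for what counts as correct. Four items in those tables are scored against a set of several codes that must be ticked together:

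- HCP B2: "Majority of HCPs selecting codes 1, 2 and 3"
- HCP B6: "Majority of HCPs selecting codes 1 & 3"
- Patient B3: "Majority of patients selecting Code 1, 3 & 4"
- Patient C5: "Majority of patients selecting Code 2, 3 and 4"

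B2, B6 and B3 carry a select-all instruction. For B6 the text runs "what are the appropriate steps that should be taken? Select all that apply 1. Infusion is immediately discontinued", and the next option is "2. Infusion is completed and IAR recorded in the logbook". C5 is printed without that instruction, but a key of three codes implies multiple selection.

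No key says that the listed codes must be the only ones ticked. HCP item A2, also a select-all item, is keyed "Majority of HCPs selecting Code 2".

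**The concern.** On a tick-list test, knowledge shows both in choosing the keyed statements and in leaving the others alone. The keys for B6, B3 and C5 test only the first. Taking the protocol's own key as given, an HCP who ticks B6 codes 1, 2 and 3 has endorsed both stopping and completing the infusion and still meets the criterion. A patient who ticks C5 codes 1 to 4 is in the same position. A patient who ticks all five statements in B3 passes, although the key treats two of them as not true.

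These are direct knowledge items, and B6 and C5 are the ones that address actions in case of an adverse event, which section 7 names within the primary objective. Counting over-selection as knowledge would favour a positive outcome on exactly these items.

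**Working it through.** **1. The plan's own figures.** The scoring question changes none of them. With half-width = 1.96 × √(p(1−p)/n), n = 34 gives 13.4, 15.4 and 16.5 points at 80, 70 and 60% (Table 6). n = 18 gives 18.5, 20.0, 21.2 and 22.6 points at 80, 75, 70 and 60% (Table 7). All rows reproduce; the 95% level is inferred from the match. What is at issue is who is counted in p.

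**2. Which answers pass.** Leaving aside the don't-know, none-of-these and not-applicable options, an item with k statements has 2^k tick patterns. The patterns containing every keyed code number 2^(unkeyed statements).

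| Item | Statements | Keyed | Unkeyed | Patterns | Pass as written | Of these, with an unkeyed statement |
|---|---|---|---|---|---|---|
| HCP B6 | 3 | 1, 3 | 2 | 8 | 2 | 1 |
| Patient B3 | 5 | 1, 3, 4 | 2, 5 | 32 | 4 | 3 |
| Patient C5 | 4 | 2, 3, 4 | 1 | 16 | 2 | 1 |
| HCP B2 | 3 | 1, 2, 3 | none | 8 | 1 | 0 |

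The exact-match answers are a subset of those that pass as written, so the literal rule can never give a lower percentage on the same data. The counts show which answers pass, not how often respondents give them. B2 scores the same under either rule.

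**3. Is the literal reading the natural one?** In A2 the same form of words on a select-all item has to be inclusive: an HCP who received the guide and also the product characteristics satisfies it. That supports an inclusive reading elsewhere in the table but does not prove it, because A2 has no wrong options. The wording is also loose in another way: on the four-point frequency scales the keys join codes 1 and 2 with an ampersand, which there can only mean either one.

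**4. Sensitivity of the threshold.** More than 70% requires 24 of 34 HCPs (70.6%; 23/34 = 67.6%) or 13 of 18 patients or caregivers (72.2%; 12/18 = 66.7%). At 23 or 12 exact answers, one over-selecting respondent changes the result for the item.

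**5. Illustration on assumed rates.** Neither the share ticking exactly the keyed set nor the share adding an unkeyed statement is in the protocol; both are assumptions. The chance of a positive outcome is P(X ≥ 24) for Binomial(34, p) or P(X ≥ 13) for Binomial(18, p). Here p is the exact share, or the exact share plus the over-selectors.

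| n | Exact share | Exact-match scoring | +5% over-selectors | +10% | +15% | +20% |
|---|---|---|---|---|---|---|
| 34 | 50% | 1.2% | 4.7% | 13.8% | 31.3% | 55.4% |
| 34 | 60% | 13.8% | 31.3% | 55.4% | 78.9% | 93.8% |
| 34 | 65% | 31.3% | 55.4% | 78.9% | 93.8% | 99.1% |
| 18 | 50% | 4.8% | 10.8% | 20.9% | 35.5% | 53.4% |
| 18 | 60% | 20.9% | 35.5% | 53.4% | 71.7% | 86.7% |
| 18 | 65% | 35.5% | 53.4% | 71.7% | 86.7% | 95.8% |

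**6. B6 against C5.** B6 code 2 is one option holding two statements: the infusion is completed, and the reaction is recorded in the logbook. In C5 logbook recording is a separate option and is keyed. An HCP who wants to indicate recording in B6 can do so only by also endorsing completion, so a tick on code 2 has no single meaning.

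**The case against.** The strongest reply is that the protocol never says over-selectors are correct. On a select-all item, and on one asking which statements are true, the listed codes can be read as the complete answer, and an analysis plan could say so. This stands in part: inclusive scoring is an inference from the wording. But the protocol itself sets the criterion, and as written it is met by a respondent who ticks too much.

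Second, section 8.8.1 provides live prompts for illogical answers and review of suspect respondents. These help, but the prompts only ask the respondent to look again and their content is not given. The named in-field checks cover repeated patterns, straight-lining on rating scales and speed, not over-selection on tick lists.

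Third, an HCP may tick B6 code 2 for its logbook half, so calling that answer contradictory is unsafe. This stands, and is why the option must be reconciled with C5 before stricter scoring is applied.

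Fourth, pattern counts and assumed rates are not evidence of frequency. This also stands; many respondents may never tick conflicting options.

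A reader might further infer that C5 could score 0% because the select-all instruction is missing. The documents do not support that: the three-code key implies multiple selection, the questionnaires are in appendices not shown, and the patient survey is piloted and soft-launched.

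**Conclusion.** The point holds for B6, B3 and C5, which are 3 of the 19 items in Tables 8 and 9. Read literally, their keys count a respondent who also ticks an unkeyed statement, including one that conflicts with a keyed answer. The effect runs in one direction, upward, and its size cannot be estimated from the documents. The binomial figures show only that modest over-selection could matter at these sample sizes if it occurred.

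Two stronger conclusions might be drawn and should not be. One is that the study objective cannot be answered: training and logbook implementation rest on other items, and the three affected items would be biased upward or ambiguous, not empty. The other is that the scoring rule inflates B2: it scores the same either way. B2's weakness is a separate one of item design. Apart from the don't-know option it has no wrong answer, so ticking every substantive box is always correct and the item discriminates weakly.

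**What to change.** - State in section 8.7 that, for B6, B3 and C5, correct means all keyed codes ticked and no unkeyed statement ticked. Report the share ticking each unkeyed statement alongside.
- Before applying this to B6, reconcile its code 2 with the C5 key, for example by listing completion of the infusion and logbook recording as separate options. This concerns item construction and scoring only; no view is taken on which clinical action is right.
- Secondary: add plausible unkeyed options to B2, and confirm that the fielded C5 carries the select-all instruction.

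The cost is a sentence on scoring, small edits to a few items and re-translation of a few lines. The scoring sentence could be added later, but the option changes have to be made before fieldwork. Reported percentages may be somewhat lower under the stricter rule.

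### HCP item B6 ties recording a reaction to completing the infusion in one unkeyed option, so it cannot show whether HCPs know to record a reaction and can misclassify those who tick that option for the logbook

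*Protocol*

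**What the plan says.** Item B6 in Table 8 (Protocol, Section 8.7) is a multi-select knowledge question: "In the event of an infusion associated reaction (IAR) what are the appropriate steps that should be taken? Select all that apply". It has four options. Code 1 is "Infusion is immediately discontinued", code 2 is "Infusion is completed and IAR recorded in the logbook", code 3 is a call to the treating physician and code 4 is don't know. The criterion is "Majority of HCPs selecting codes 1 & 3". Table 8 does not say how a respondent who ticks code 2 as well as 1 and 3 is scored.

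Item C5 in Table 9 puts a comparable situation to patients and caregivers, a patient who "developed a headache and a fever during the infusion". There the actions are listed one by one. Completing the infusion is code 1 ("Complete the infusion and then rest"), stopping is code 2, contacting the physician is code 3 and "Record details in the logbook" is code 4. The criterion is "Majority of patients selecting Code 2, 3 and 4". Item C6 in the same table keys only the unconditional yes to reporting a side effect in the logbook.

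Section 8.7 defines a positive outcome as more than 70% of participants giving a correct response. Section 7 lists actions in case of an adverse event among the content areas of the primary objective.

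**The concern.** Code 2 of B6 asks about two actions at once. Its first half is the opposite of keyed code 1. Its second half is an action that the patient survey keys as correct. An HCP who holds that the infusion is stopped, the physician called and the reaction recorded has no way to give that answer: the choice is to tick code 2, and so also endorse completing the infusion, or to leave recording out.

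B6 is the only item in Table 8's category on knowledge of actions in an IAR or AE. B5c scores how often training covers the topic. B5d, C1, C2 and C4 score logbook training and logbook practice. None of them asks whether a reaction has to be recorded. At stake is whether the B6 percentage can be read as knowledge of what to do in a reaction. Once the data are in, the two meanings of a code 2 tick cannot be separated by any scoring rule.

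**Working it through.** **Inputs.** HCP sample 34 (Section 8.5.1); positive outcome above 70% (Section 8.7); B6 key 1 and 3 (Table 8); C5 key 2, 3 and 4 (Table 9). The share of HCPs who know the two keyed steps, and the share of those who would also tick code 2 for the logbook, are not in the protocol. They are assumed below: 80% to 90% for the first (80% is one of the levels in Table 6), 0% to 20% for the second.

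**The plan's own figure.** Table 6 follows from p ± 1.96 × √(p(1−p)/n). At p = 0.80 and n = 34: 1.96 × √(0.16/34) = 0.134, giving 66.6% to 93.4%, as printed. The 70% and 60% rows also reproduce. No stated figure is in dispute.

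**Step 1: what B6 can and cannot separate.**

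| What the HCP holds | Codes ticked | Extra codes disqualify | Extra codes ignored |
|---|---|---|---|
| Stop, call, record | 1+3 | correct | correct |
| Stop, call; unaware of recording | 1+3 | correct | correct |
| Stop, call, record; code 2 ticked for the logbook | 1+2+3 | wrong | correct |
| Self-contradictory: stop and also complete; call | 1+2+3 | wrong | correct |

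Rows 1 and 2 give the same data, so B6 carries no information on recording. Rows 3 and 4 also give the same data, so either rule treats a knowledgeable HCP and a confused one alike.

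**Step 2: the pass mark.** 0.70 × 34 = 23.8, so 24 correct are needed (24/34 = 70.6%; 23/34 = 67.6%).

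**Step 3: sensitivity if extra codes disqualify.** Let k be the share who know the keyed steps and s the share of those who also tick code 2 for the logbook. The expected correct rate is p = k(1 − s), and the chance of a positive result is the exact binomial P(X ≥ 24 | 34, p).

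| k | s | p | P(positive) |
|---|---|---|---|
| 0.80 | 0 | 0.80 | 93.8% |
| 0.80 | 0.10 | 0.72 | 65.5% |
| 0.80 | 0.125 | 0.70 | 55.4% |
| 0.80 | 0.20 | 0.64 | 27.1% |
| 0.90 | 0.10 | 0.81 | 95.5% |
| 0.90 | 0.20 | 0.72 | 65.5% |

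The expected rate reaches 70% at s = 1 − 0.70/k, which is 12.5% for k = 0.80 and 22.2% for k = 0.90.

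**Step 4: what B6 leaves unseen.** Take k = 0.80 and suppose that 20% of those HCPs do not know that a reaction is to be recorded. If nobody ticks code 2, B6 still gives a positive result with probability 93.8%. A three-action key of the C5 type would have p = 0.80 × 0.80 = 0.64 and a probability of 27.1%. This shows only how much the choice of action set can matter.

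**The case against.** Three stronger readings are tempting, and the protocol does not support them.

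**That B6 misclassifies HCPs.** An HCP who would stop, call and record can tick 1 and 3 and is scored as the key intends; leaving recording out costs nothing. Misclassification needs an answer that includes both codes 1 and 2, whose first actions contradict each other. Code 2 can be read as a deliberate distractor. Section 8.8.1 provides live prompts on illogical answers and a soft launch with one HCP per country, either of which may catch some such answers. The full questionnaire (Appendix 1) is only listed, so scripted exclusivity between codes 1 and 2 cannot be ruled out. All of this stands, and the supported wording is that B6 can misclassify. None of it lets an HCP select recording alongside stopping, and the debriefed pilot in Section 8.8.1 covers only the patient/caregiver survey.

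**That the item could come out negative although every HCP knows the steps.** This is arithmetically possible: if 11 of 34 (32%) ticked code 2 only for the logbook and were disqualified, at most 23/34 = 67.6% could be correct. Nothing in the protocol suggests that so many would.

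**That the two surveys must share one key.** Section 8.1 describes them as independent, and no planned analysis sets B6 beside C5. Section 7 describes the logbook as belonging to the patient and reviewed by the HCP, which could justify different keys. But B6 asks in general what should be done, its code 3 names the patient or infusion nurse as the caller, and Section 8.1.1 includes nurses in the HCP sample. The difference therefore calls for a stated reason; it is not in itself an error.

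Scoring of extra codes may also be settled in an analysis plan that is not shown. That would fix the rule but would not separate the two meanings of a code 2 tick.

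**Conclusion.** The point holds as a defect in one response option. B6 cannot show whether an HCP knows that a reaction is to be recorded, and an answer that includes code 2 cannot be interpreted under either scoring rule. This affects the only scored HCP knowledge item on actions in a reaction, which is one of ten questions in Table 8 and falls within a primary-objective content area.

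The size is unknown, because the number who would tick code 2 cannot be taken from the protocol. Under strict scoring and assumed knowledge of 80%, a 10% to 20% share ticking code 2 lowers the chance of a positive result from 93.8% to between 65.5% and 27.1%. At 90% knowledge, a 10% share leaves it at 95.5%. Severity is should-fix: the analysis is descriptive, no stated figure is wrong, and the repair is cheap before fieldwork.

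**What to change.** Before fieldwork:

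1. Split code 2 of B6 into two single-action options, one for completing the infusion and one for recording the IAR in the logbook.
2. State in Table 8 whether selecting codes beyond the key makes an answer incorrect.
3. Reconcile the B6 key with patient items C5 and C6 against the approved educational materials, or state why the HCP and patient keys differ. Which actions are right is for the sponsor to settle from those materials.

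The cost is one extra answer line in the HCP questionnaire, its translation, and one edit to the key in Table 8. No sample size or precision figure changes.
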